2.3.1 Risk assessment	Clarify mitigation strategy for anaphylaxis	For clarity and alignment across protocol sections
5.2 Exclusion criteria	Update exclusion criterion 11f (creatinine)	Allow inclusion based on normal creatinine values, as well as sufficient GFR, as AL101 is not expected to impact renal function
6.4 AL101 Dose modification and toxicity management guidelines (Table 3) 6.4.4 Guidelines of the management of colitis (Table 4)	Introduce change in regimen (2 weeks on / 1 week off) for first episode of Grade 2 or 3 diarrhea and Grade 2 Colitis before dose reduction on subsequent episodes	To allow investigators to use a 2 weeks on 1 weeks off regime at 6 mg QW, before implementing dose reduction. The aim is to introduce a scheduled dose interruption to prevent recurrence of toxicity
6.4 AL101 Dose modification and toxicity management guidelines (Table 3) 10.2, Appendix 2 Clinical laboratories	Add lipase for subjects experiencing \geq Grade 2 diarrhea adverse events	Per request of the Spanish competent authority

Section	Summary of Change	Rationale for Change
6.4.1 Treatment of infusion reactions 8.3.5 Adverse events of special interest 10.3.2 Definition of SAE	Emphasize that Grade 3 or 4 infusion reactions should be reported as SAE. Clarify that all infusion reactions must be reported as adverse events of special interest.	To ensure sites are aware of these reporting requirements
7.2 Discontinuation of investigational product	Clarify that subjects being managed with dose interruption for toxicity should have their study assessments followed per SoA.	For continued care and safety of subject during the dose interruption
9 Statistical considerations	Clarify the 4 responses in Stage 1 will trigger Stage 2 Clarify efficacy evaluable analysis population	For consistency and clarity
General	Correct typos, hyperlinks, style and formatting Align across protocol sections	For consistency and clarity

TABLE OF CONTENTS

CLINICAL STUDY PROTOCOL	1
APPROVALS	2
PRINCIPAL INVESTIGATOR SIGNATURE PAGE	3
CURRENT PROTOCOL AMENDMENT SUMMARY OF CHANGES	4
1. PROTOCOL SUMMARY.....	11
1.1. Synopsis.....	11
1.2. Study Schema	15
1.3. Schedule of Activities (SoA).....	16
2. INTRODUCTION	21
2.1. Study Rationale.....	21
2.2. Background.....	21
2.3. Benefit/Risk Assessment	22
2.3.1. Risk Assessment.....	22
2.3.2. Benefit Assessment.....	23
2.3.3. Overall Benefit Risk Conclusion	23
3. OBJECTIVES AND ENDPOINTS	24
4. OVERALL STUDY DESIGN.....	26
4.1. Study Design.....	26

1. PROTOCOL SUMMARY

1.1. Synopsis

Protocol Title

TENACITY: A Phase 2, Multicenter, Open-label, Single-arm Study of AL101 Monotherapy in Patients with Notch-activated Triple Negative Breast Cancer

Study Rationale and Hypothesis

AL101 is a potent and selective inhibitor of gamma secretase-mediated Notch signaling that is currently under development as an antitumor/antiangiogenic agent as monotherapy for the treatment of various cancers. A large body of experimental evidence supports the causal role of Notch pathway deregulation in cancer development and progression ([Previs, 2015](#); [Wang, 2015b](#); [Braune, 2016](#); [Vinson, 2016](#); [Xiao, 2016](#); [Zhao, 2017](#)).

Triple negative breast cancer (TNBC) is a heterogeneous disease entity constituting about 15% of newly diagnosed breast cancer (BC) cases and a higher percentage of metastatic BC cases worldwide. TNBC is associated with poor prognosis and lack of sustained response to conventional chemotherapeutic agents ([Rouzier, 2005](#); [Dua, 2017](#); [Polk, 2017](#)). Patients with recurrent and/or metastatic TNBC have a median survival of approximately 13-24 months ([Kassam, 2009](#); [Steponaviciene, 2011](#)); therefore, there is an urgent need to identify new therapeutic strategies for these patients.

The Notch pathway is activated during mammary gland development and has been implicated as a key driver in BC ([Collu, 2007](#)). The frequency of Notch mutations or gene rearrangement was reported at 5 to 16% in small cohorts of TNBC tumors and high level of Notch expression was associated with poorer overall survival ([Robinson, 2011](#); [Stoeck, 2014](#); [Wang, 2015a](#)). In addition, elevated Hes4 expression, a marker of Notch activation, is associated with poorer prognosis in TNBC ([Stoeck, 2014](#)).

In nonclinical models, AL101 has a broad-spectrum antitumor activity against solid tumor xenografts of diverse histological types at tolerable doses, including breast carcinoma. AL101 exerted its antitumor activity through direct inhibition of cell proliferation and indirectly via inhibition of tumor angiogenesis. In TNBC patient-derived xenograft (PDX) tumor models, the presence of activating Notch mutations/fusions correlated with potent response to AL101 monotherapy.

The current study is designed to evaluate the efficacy and safety of AL101 monotherapy in subjects with Notch-activated recurrent or metastatic TNBC; Notch activation will be determined by a Next Generation Sequencing (NGS) test.

Objectives and Endpoints (Primary and Secondary only)

Objectives	Endpoints
Primary	

 To evaluate the efficacy of AL101 monotherapy in subjects with Notch-activated recurrent or metastatic TNBC 	
 Proportion of subjects who demonstrate an overall response rate (ORR) defined as partial response (PR) + complete response (CR) as assessed by investigator based on Response Evaluation Criteria in Solid Tumors (RECIST) v1.1
Secondary	

 Efficacy - Secondary 	
 Clinical benefit response rate (CBR) defined as CR + PR + stable disease (SD) by investigator review based on RECIST v1.1 Duration of response (DOR) by investigator review based on RECIST v1.1 Progression free survival (PFS) Proportion of subjects who have PFS at 6 months Overall survival (OS) Quality of life (QoL) as determined by European Organization for Research and Treatment of Cancer Quality of Life Questionnaire 30 questions (EORTC QLQ-C30) and Breast Cancer 45 questions (EORTC QLQ-BR45)

 To evaluate the safety and tolerability of AL101 monotherapy in subjects with recurrent or metastatic TNBC 	
 Frequency, duration and severity of treatment-emergent adverse events (TEAEs) and serious adverse events (SAEs) Incidence of clinically significant abnormalities in laboratory parameters, electrocardiograms (ECGs), vital signs and physical examination

Overall Design

This is an open-label, multicenter, Phase 2, Simon two-stage optimal design for targeted therapy study of single arm AL101 monotherapy in subjects with Notch-activated recurrent or metastatic TNBC whose disease has recurred or progressed after 3 or fewer lines of prior therapy.

The design will include a lead-in cohort with 6 subjects to ascertain safety of the investigational product (IP), AL101, 6 mg weekly (QW). The safety will be reviewed on a regular schedule (weekly calls with investigators, and quarterly reviews with the Data Monitoring Committee [DMC]). After the 6th subject is enrolled and completes 4 weeks of therapy (1 cycle), the results will be reviewed in aggregate and, if the safety is acceptable (as defined below), the study will continue at 6 mg administered QW. Note, if safety is not acceptable amongst the first 6 subjects dosed at 6 mg QW, the IP dose will be reduced to 4 mg QW. The decision on which dose to use for the remainder of the study will be determined after a formal safety assessment with the investigators and the DMC.

Acceptable safety:

- 2 or fewer subjects experience Grade 3 or 4 diarrhea lasting more than 3 days
- 2 or fewer subjects experience another specific Grade 3 or 4 adverse event (AE) which is attributable to IP

After the lead-in phase with AL101 6 mg QW, the study will proceed to complete the described Simon two-stage design as shown in [Figure 1](#) and described in Section [9.1](#).

Prior to entering the study, to determine eligibility, potential candidates who sign a separate pre-screening informed consent, will undergo pre-screening assessment for evaluation of Notch mutational status from a persistent locally advanced or metastatic lesion.

After signing an informed consent, all subjects will then undergo screening assessments to determine study eligibility over a 28-day Screening period, including TNBC molecular characterization. Eligibility criteria for study entry will be assessed locally by the investigator; radiographic scans at screening and from the prior 12 months will be collected and held for possible future retrospective independent evaluation.

Starting on Cycle 1, Day 1, eligible subjects will be treated with IP intravenously (IV) QW, on Days 1, 8, 15 and 22 of each 28-day cycle. Treatment will continue until the occurrence of unequivocal radiographic disease progression per RECIST v1.1 as assessed by the investigator, or clear clinical progression as assessed by the investigator, or unacceptable toxicity, or other reasons for discontinuation.

All subjects will receive premedication with H1- and H2-blockers (refer to Section [6.6.1](#)) and corticosteroids as prophylaxis (refer to Section [6.6.2](#)). Toxicity post-AL101 administration will be managed as specified in Section [6.4](#).

During the treatment period, subjects will undergo radiographic assessments every 8 weeks (± 3 days) for review by the investigator. Radiographic scans will also be collected and held for possible future retrospective independent evaluation. Other assessments will be done as specified in the Schedule of Activities ([Table 1](#)). A repeat of tumor imaging will be required for the purposes of confirmation of response (i.e., partial response, and/or complete response). The confirmation scan should be no earlier than 4 weeks following the first indication of response.

Samples from tumor biopsies will be collected at screening from a locally advanced or metastatic lesion (fresh or archival within 2 years), and at Cycle 4 Day 1 ±28 days (provided that biopsy collection is medically safe and not contraindicated). If an archival tumor block or 25 unstained slides are not available, the subject will be required to have a fresh tumor sample obtained at screening. Biopsy samples will be evaluated by NGS for genomics, immunohistochemistry (IHC) for Notch intracellular domain (NICD) stain, and other biomarkers potentially related to sensitivity to AL101 or TNBC prognosis. Blood samples for pharmacokinetics (PK) and biomarker analysis will also be collected on the same day as the on-treatment biopsy.

All subjects will undergo end of study (EOS) visit 30 days post last treatment with IP and will be contacted to determine survival status at timepoints specified in study duration. In subjects who discontinued IP due to toxicity, radiographic imaging will be done every 3 months until disease progression or until the subject initiates another anti-cancer therapy.

Disclosure Statement

This is a single group treatment study with no masking.

Number of Subjects

Using the Simon two-stage optimal design (targeting a response of 23% or greater), up to 67 to 73 subjects will be enrolled, depending on IP dose evaluated in Stage 1 and Stage 2 as follows:

- if the AL101 dose is 6 mg QW throughout the study, there will be up to 67 subjects evaluated, including the 6 subjects in the lead-in cohort for the Stage 1 evaluation.
- if AL101 4 mg is evaluated in Stage 1 and Stage 2, there will be up to 73 enrolled subjects consisting of up to 67 subjects at AL101 4 mg and 6 subjects in the lead-in cohort of AL101 6 mg. Note, the lead-in cohort will not be included in the Stage 1 evaluation.

In both scenarios there will be up to 26 evaluable subjects in Stage 1, and 41 additional evaluable subjects in Stage 2 provided at least 4 subjects (out of 26) responded in Stage 1 ([Table 8](#)).

Intervention Group

Lead-in phase: AL101 6 mg IV administered QW, on Days 1, 8, 15 and 22 of each 28-day cycle

Main Study: AL101 4 or 6 mg IV administered QW, on Days 1, 8, 15 and 22 of each 28-day cycle

Study Duration for Each Subject

[figure not shown]
For each subject, the study is expected to last as follows:

Screening period:	Up to 28 days
Treatment period:	Until disease progression, unacceptable toxicity, or consent withdrawal
EOS:	30 days after the last administration of IP
Long term follow-up:	Every 3 months for the first year after EOS, then every 6 months for the next 2 years and then annually.

Data Monitoring Committee: Yes

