9. STATISTICAL CONSIDERATIONS

9.1. Statistical Hypothesis and Sample Size Determination

The study will utilize the Simon two-stage optimal design (Figure 1 and Table 8) and will include up to 67 to 73 subjects, depending on IP dose evaluated in Stage 1 and Stage 2 as follows:

- if the AL101 dose is 6 mg QW throughout the study, there will be up to 67 subjects evaluated, including the 6 subjects in the lead-in cohort for the Stage 1 evaluation.
- if AL101 4 mg is evaluated in Stage 1 and Stage 2, there will be up to 73 enrolled subjects consisting of up to 67 subjects at AL101 4 mg and 6 subjects in the lead-in cohort of AL101 6 mg. Note, the lead-in cohort will not be included in the Stage 1 evaluation.

In both scenarios there will be up to 26 evaluable subjects in Stage 1, and 41 additional evaluable subjects in Stage 2 provided at least 4 subjects (out of 26) responded in Stage 1.

While the data on Stage 1 is maturing, Stage 2 will continue enrolling an additional 41 subjects, unless an unexpected safety signal emerges that in the judgement of the DMC requires analysis and/or poses a serious threat to the well-being of the subject. This decision will be made in agreement with the Sponsor.

If no more than 3 subjects respond in Stage 1, the study will be stopped for futility. If 4 or more subjects respond, Stage 1 will be considered positive. For the entire study (Stages 1 and 2), the null hypothesis will be rejected if 15 or more responses are observed in 67 subjects. Only the Efficacy Evaluable set of subjects will be counted toward this analysis. This design has 80% power at the 5% type I error level to detect a desirable success rate of 23% against the null hypothesis of an unacceptable success rate of 11%. The success rate parameters for the two-stage design are aligned with recent published experience of clinical studies (Twelves, 2014). If at the end of Stage 1, there are 4 responses in the Notch-activated TNBC subjects, the study will continue to Stage 2.

Table 8 Sample Size Hypothesis

Total	Look1	Futility Boundary		Attained	Attained	Probability of	Expected
							Sample Size
(n)	(n_1)	Look1	Look2	Alpha	Power	Early	H0 (EN0)
		(r_1)	(r_2)			Stopping	
67	26	3	11	0.049	0.807	0.681	39.1

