9.4. Interim Analyses

Because a Simon two-stage optimal design will be employed, ORR will be assessed during Stage 1 for subjects who have received IP for at least 2 cycles (8 weeks) and no more than 8 cycles (8 months). While the data on Stage 1 is maturing, Stage 2 will continue enrolling an additional 41 subjects for a total of 67 subjects, unless an unexpected safety signal emerges that in the judgement of the DMC requires analysis and/or poses a serious threat to the well-being of the subject.

The Statistical Analysis Plan will describe the planned analyses in greater detail.

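### The figure 67 serves both as the enrolment at the study dose and as the evaluable count for the Simon test, so the stated 80% power has no margin for non-evaluable subjects

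*Combined protocol and SAP*

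**What the plan says.** On enrolment, the synopsis states "up to 67 to 73 subjects will be enrolled, depending on IP dose evaluated in Stage 1 and Stage 2 as follows". In the 4 mg scenario the 73 splits into up to 67 at 4 mg and 6 lead-in subjects at 6 mg who do not enter the Stage 1 evaluation. Section 9.4 says "Stage 2 will continue enrolling an additional 41 subjects for a total of 67 subjects".

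On the test, the synopsis and Section 9.1 say "In both scenarios there will be up to 26 evaluable subjects in Stage 1, and 41 additional evaluable subjects in Stage 2", provided Stage 1 has at least 4 responders. Section 9.1 adds: "Only the Efficacy Evaluable set of subjects will be counted toward this analysis".

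On the decision rule, Section 9.1 says "If no more than 3 subjects respond in Stage 1, the study will be stopped for futility" and "the null hypothesis will be rejected if 15 or more responses are observed in 67 subjects". Table 8 gives n = 67, n1 = 26, r1 = 3, r2 = 11, attained alpha 0.049 and power 0.807. An r2 of 11 means rejecting at 12 or more.

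On who counts, Section 9.2 requires a dose of product at the dose settled by the lead-in, measurable disease, and at least one post-baseline tumour assessment. Subjects with documented early clinical or radiological progression are kept without one. A subject whose local and central Notch results disagree is non-evaluable.

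**The concern.** Enrolled and evaluable totals are set equal, while Section 9.2 gives two routes by which a treated subject drops out of the evaluable set: no post-baseline assessment without documented early progression, and a discordant central Notch result. Subjects may enter on a local or historical assay (Section 4.1), so discordance can emerge after enrolment.

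If any of the 67 are lost, the test runs on fewer subjects than it was designed for. Keeping the count fixed for 67 makes it stricter than planned and lowers power. Changing the count means choosing a cut-off that the supplied text does not define. Section 9.3 finalises the SAP only before database lock, so in an open-label study that choice could be made with the responses in view.

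**Working it through.** **Inputs.** From Section 9.1 and Table 8: p0 = 0.11, p1 = 0.23, n1 = 26, r1 = 3, n = 67, r2 = 11 (reject at R = 12). The documents give no non-evaluable rate, so the rates below are assumptions.

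**Formula.** P(reject | p) = sum over x = 4 to n1 of b(x; n1, p) × P[Bin(n − n1, p) ≥ R − x]. Alpha takes p = 0.11 and power takes p = 0.23.

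**Reproducing Table 8** (n1 = 26, n = 67, R = 12):
- alpha 0.0494 (stated 0.049)
- power 0.8069 (stated 0.807)
- probability of early stopping under the null 0.681 (stated 0.681)
- expected sample size 26 + (1 − 0.6807) × 41 = 39.1 (stated 39.1)

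With the text's cut-off of 15 or more, alpha is 0.0051 and power 0.573 at the full 67. The 80% claim therefore belongs to Table 8's rule, which is used from here on.

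**Loss in Stage 2 only** (n1 = 26, R = 12):

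| Evaluable n | Loss from 67 | Alpha | Power |
|---|---|---|---|
| 67 | 0 | 0.049 | 0.807 |
| 66 | 1 (1.5%) | 0.046 | 0.797 |
| 65 | 2 (3.0%) | 0.042 | 0.787 |
| 64 | 3 (4.5%) | 0.038 | 0.775 |
| 60 | 7 (10.4%) | 0.026 | 0.717 |

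**Loss in both stages** (r1 = 3 and R = 12 kept):
- 25 then 64 (about 5%): power 0.762
- 23 then 60 (about 10%): power 0.676, or 0.737 if the cut-off is re-derived to 11 or more

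The chance of a wrong futility stop at a true rate of 23% is 12.0% with n1 = 26, 14.0% with 25 and 19.0% with 23.

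**Chance of full evaluability.** If each of 67 subjects is independently non-evaluable with probability 5%, all 67 are evaluable with probability 0.95^67 = 0.032, and at least 66 with probability 0.146.

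**Smallest cut-off with alpha at or below 0.05** (3/26 look kept):
- n = 53 to 59: 11 or more. Alpha is 0.0472 at 59, where power is 0.777. At 60 the same count gives alpha 0.0516, which is too high.
- n = 60 to 67: 12 or more. Alpha is 0.0494 at 67.
- n = 68: 12 or more gives 0.0535, so 13 or more is needed (alpha 0.028, power 0.762).

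**The case against.** The strongest reply is that 67 already means evaluable. The 6 mg bullet speaks of subjects evaluated, the 26 + 41 are called evaluable, and the counting rule is explicit. That stands as far as it goes: the evaluable target is in the text. But the synopsis and Section 9.4 attach the same number to enrolment, and nothing provides for enrolling more.

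A reader might infer that enrolling 67 must leave fewer than 67 evaluable. The documents do not support that. Early progressors are retained, measurable disease is an entry criterion, and Section 8.4.1 says only that local Notch results may be confirmed centrally (Section 4.1 does mention confirmatory testing). Loss is likely, not certain, and its size is unknown.

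A reader might also infer a raised false-positive risk. The reverse holds: with 12 or more kept, alpha falls as n falls. The risk exists only above 67.

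Three further points stand. One loss gives 0.797, which still rounds to 80%. For 60 to 67 evaluable the correct cut-off remains 12, so a missing table changes no decision there if Stage 1 has 26. And the conflict between 15 and 12 is larger than this issue.

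Finally, the detailed SAP is deferred and Figure 1 is not shown, so the statement that no other cut-off is given applies to the supplied text.

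**Conclusion.** The point holds as an inconsistency and an omission; Table 8 itself is computed correctly. Under Table 8's rule, attained power is at or above 0.80 only with all 67 evaluable. Assumed losses of about 5% and 10%, all in Stage 2, bring it to 0.775 and 0.717. If Stage 1 loses subjects too, the 5% case becomes 0.762. The cost is lost power, with no inflation of alpha.

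These figures rest on Table 8's r2 = 11 being the intended boundary. If the text's 15 or more is intended, power is 0.573 even with no loss, and evaluability is the lesser problem.

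**What to change.** 1. First reconcile Section 9.1's final cut-off of 15 or more with Table 8's r2 = 11. The cut-offs in step 4 apply only if Table 8 is confirmed.
2. State in the synopsis and Sections 9.1 and 9.4 that 26 and 67 are Efficacy Evaluable counts, and give the enrolment figure separately.
3. If enrolment stays at 67, restate power as about 0.72 to 0.78 for 5 to 10% non-evaluable, noting that this assumes 26 evaluable in Stage 1. The alternative is an enrolment allowance or replacement rule: 67/0.95 = 70.5, so 71 subjects at 5%, or 67/0.90 = 74.4, so 75 at 10%.
4. Pre-specify that the final cut-off is the smallest count with exact two-stage alpha at or below 0.05 at the attained Stage 1 and final evaluable numbers. With 3/26 kept: 11 or more for 53 to 59, 12 or more for 60 to 67, 13 or more at 68.
5. State how Stage 1 is judged if fewer than 26 are evaluable.

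Cost: wording and a short table. Keeping enrolment at 67 needs no extra patients but means accepting a lower stated power. The allowance adds 4 subjects at 5% or 8 at 10%.

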1.2. Study Schema

Figure 1 Study Schema based on Simon's Two-Stage Optimal Design for Targeted Therapy

1.3. Schedule of Activities (SoA)

Table 1 Schedule of Activities

Assessments	Pre-Screen ^a	Screening Period (days)	Treatment Period ^a (by cycles and days of cycle)												End of Study (EOS) Visit	Long-Term Follow-up ^o
			Cycle 1				Cycle 2				Cycles 3+					
		-28 to -1	D1	D8	D15	D22	D1	D8	D15	D22	D1	D8	D15	D22	30 days post last investigational product	
Prescreen informed consent	X															
Informed consent		X														
NGS Assay	X ^b															
Tumor biopsy ^c		X										Cycle 4 (±28 days) only				
Medical & breast cancer disease history (including therapy and prior scans)		X														
Concomitant medications		X	X	X	X	X	X	X	X	X	X	X	X	X	X	
Complete physical exam ^d		X	X									X every odd cycle or as clinically indicated				X
Symptoms directed PE				X	X	X	X	X	X	X	X	X every even cycle	X	X	X	
Vital signs		X	X	X	X	X	X	X	X	X	X	X	X	X	X	
Height		X														
Weight		X	X	X	X	X	X	X	X	X	X	X	X	X	X	
ECOG performance status		X	X	X	X	X	X	X	X	X	X	X	X	X	X	
CBC w/diff, platelets ^e		X	X	X	X	X	X	X	X	X	X	X	X	X	X	
Serum chemistry ^f		X	X ^g	X ^h	X ^h	X ^h	X									

Assessments	Pre-Screen ^a	Screening Period (days)	Treatment Period ^a (by cycles and days of cycle)												End of Study (EOS) Visit	Long-Term Follow-up ^o
			Cycle 1				Cycle 2				Cycles 3+					
		-28 to -1	D1	D8	D15	D22	D1	D8	D15	D22	D1	D8	D15	D22	30 days post last investigational product	
Lipid panel ^q			X				X				X					
Thyroid function (TSH, T3, T4)			X								X (every 12 weeks)					
HbA1c			X								X (every 12 weeks)					
HIV, Hepatitis B and C by history		X														
Coagulation factors		X	X								X ⁱ (every 8 weeks)					
Urinalysis ^j		X													X	
Pregnancy test ^k		X	X				X				X				X	
12 lead ECG ^l		X									X (every 12 weeks)				X	
AL101 infusion			X	X	X	X	X	X	X	X	X	X	X	X		
Adverse events		X	←-----X-----→												X	
Radiological imaging and Disease evaluation by RECIST v1.1 ^m		X									X (every 8 weeks)				X	X ^m
Brain MRI (preferred) or CT (acceptable) with contrast ⁿ		X									X (every 12 weeks) for known /suspected disease					
Blood for biomarkers		X	X (predose)				X (predose)				X (predose, every 8				X	

Assessments	Pre-Screen ^a	Screening Period (days)	Treatment Period ^a (by cycles and days of cycle)												End of Study (EOS) Visit	Long-Term Follow-up ^o
			Cycle 1				Cycle 2				Cycles 3+					
		-28 to -1	D1	D8	D15	D22	D1	D8	D15	D22	D1	D8	D15	D22	30 days post last investigational product	
															weeks) & Cycle 4 (with biopsy)	
Blood for PK ^p			X	X	X		X (predose)				X (predose, odd cycles) & Cycle 4 (with biopsy)					
Overall survival																📞 / visit ^o
EORTC QLQ-C30 and EORTC QLQ-BR45 (before infusion)		X	X				X				X				X	

Abbreviations: CBC = Complete blood count; CT = computed tomography; ECOG = Eastern Cooperative Oncology Group; EOS = end of study, EORTC QLQ-C30 = European Organization for Research and Treatment of Cancer Quality of Life Questionnaire 30 questions; EORTC QLQ-BR45 = European Organization for Research and Treatment of Cancer Quality of Life Breast Cancer Module Questionnaire 45; questions; HbA1c = glycosylated hemoglobin; HIV = human immunodeficiency virus; IHC = immunohistochemistry; MRI = magnetic resonance imaging; NICD = Notch intracellular domain; NGS = Next generation sequencing; PE = physical examination; RECIST = Response Evaluation Criteria in Solid Tumors; TSH = thyroid stimulating hormone.

Notes to Schedule of Activities:

All assessments to be performed pre-infusion unless stated otherwise.

Visit window will be ± 2 days during treatment period, except for imaging ± 3 days (if AL101 dosing is delayed by up to 7 days, then imaging can be similarly delayed); EOS and Long-term follow-up will be ± 7 days.

- a. Pre-screening assessments may be done while potential candidates are on other therapy provided that a separate pre-screening informed consent form is signed.
- b. For determining eligibility, potential candidates will undergo a pre-screening assessment to determine Notch mutation status, after signing the prescreening ICF. Available genotyping results from within the last 2 years from a commercially available or laboratory developed test (LDT) NGS assay are acceptable. If acceptable genotyping results are not available, NGS testing will need to be conducted during pre-screening using a commercially available NGS assay, LTD or other validated investigational use only (IUO) clinical trial assay using tumor biopsy from within the last 2 years. When available, NGS test results will be shared with investigators and determination of Notch mutation status and eligibility will be communicated.
- c. Tumor biopsies (a resection, or core needle or punch biopsy with 20 gauge or larger and at least 2 passes) will be collected both at screening (fresh or archival within 2 years, from the same biopsy used for pre-screening), and at Cycle 4 Day 1 ± 28 days (fresh biopsy, provided medically safe and not contraindicated). If a tumor block or 25 unstained slides are not available, the subject will be required to have a fresh tumor sample obtained at screening from a readily accessible persistent locally advanced or metastatic lesion.
- d. Complete physical examination at baseline (refer to Section 8.2.3 for body systems to be evaluated) and every odd cycle thereafter or as clinically indicated; targeted physical examination at other time points.
- e. Refer to Section 10.2 for list of parameters
- f. Refer to Section 10.2 for list of parameters
- g. Screening laboratory may be used if conducted within 3-7 days of CID1.
- h. Chemistry will be conducted every week for the first 3 cycles and then every 4 weeks, with the exception of liver function tests (aspartate aminotransferase/alanine aminotransferase/alkaline phosphatase/bilirubin) which will be done weekly until week 32, and then every 2 weeks thereafter
- i. Coagulation factors will be done on Day 1 of every other cycle (e.g., C3D1, C5D1...)
- j. Urinalysis performed at Screening and as clinically indicated. Refer to Section 10.2 for list of parameters
- k. Pre-menopausal female subjects of childbearing potential only. Urine or serum pregnancy tests are acceptable.
- l. In the event of possible abnormal ECG findings, per the discretion of the investigator, additional ECG reads could be added at follow-up visits. The ECG evaluation will be performed locally; single ECG will be collected pre-dose (within 1 hour of infusion) and post-dose (within 1 hour post end of infusion). Clinically significant ECG abnormalities will be recorded on the electronic case report form (eCRF).
- m. CT or MRI with contrast are acceptable. Refer to Table 5 for imaging requirements during the study.
- n. For known or suspected brain metastases at baseline repeat brain MRI (preferred)/CT (acceptable) with contrast every 12 weeks. Conduct brain MRI/CT with contrast when subject has clinical symptoms. Same modality should be used throughout the study.

- o. During long-term follow up, subjects will be contacted every 3 months for the first years after EOS, then every 6 months for the next 2 years and then annually
- p. PK blood samples will be collected as follows:

Cycle / Day	Hours Relative to Dose (Window)
Cycle 1 / Days 1, 8, and 22	Pre-dose (within 1 hour before start of dose) End-infusion (within 10 minutes of infusion end)
Cycle 2,3,5,7/ Day 1	Pre-dose (within 1 hour before start of dose)
Cycle 4 / Day 1 ± 28 days	On same day as on-treatment biopsy is collected

- q. Lipid panel will be taken after at least an 8 hour fast and will include: triglycerides, total cholesterol, low-density lipoprotein(LDL), and high-density lipoprotein (HDL).

